# 10 Assessment of Safety and Data Safety Monitoring Plan (DSMP)

## 10.1 Definitions

The following definitions will be used in the assessment of safety:

Adverse Event (AE) is any untoward or unfavorable medical occurrence in a human subject, including any abnormal sign (for example, abnormal physical exam or laboratory finding), symptom, or disease, temporally associated with the subject's participation in the research, whether or not considered related to the subject's participation in the research.

Serious Adverse Event (SAE) is any adverse event that

- (1) results in death;
- (2) is life-threatening;
- (3) results in subject hospitalization or prolongation of existing hospitalization;
- (4) results in a persistent or significant disability/incapacity;
- (5) results in a congenital anomaly/birth defect;
- (6) based upon appropriate medical judgment, may jeopardize the subject's health and may require medical or surgical intervention to prevent one of the other outcomes listed in this definition (examples of such events include allergic bronchospasm requiring intensive treatment in the emergency room or at home, blood dyscrasias or convulsions that do not result in inpatient hospitalization, or the development of drug dependency or drug abuse).

*Life-threatening* means that the event places the subject at immediate risk of death from the event as it occurred.

*Unanticipated Problem* is defined as an event, experience or outcome that meets **all three** of the following criteria:

- is unexpected; AND
- is related or possibly related to participation in the research; AND
- suggests that the research places subjects or others at a greater risk of harm (including physical, psychological, economic, or social harm) than was previously known or recognized.

*Possibly related* means there is a reasonable possibility that the incident, experience, or outcome may have been caused by the procedures involved in the research

*Unexpected* means the nature, severity, or frequency of the event is not consistent with either:

- the known or foreseeable risk of adverse events associated with the procedures involved in the
  research that are described in (a) the protocol–related documents, such as the IRB-approved
  research protocol, any applicable investigator brochure, and the current IRB-approved informed
  consent document, and (b) other relevant sources of information, such as product labeling and
  package inserts; or
- the expected natural progression of any underlying disease, disorder, or condition of the subject(s) experiencing the adverse event and the subject's predisposing risk factor profile for the adverse event.

## 10.2 Safety Review

[name] or [name] will interview the subjects in the intervention and sham groups before their next exposure each week for any adverse events including erythema or any other skin reactions. At the time of the evaluation, it will be determined whether the subject will continue with the next exposure or whether the subject will be removed from the study. This will be based on the determination of the degree of erythema or adverse skin reaction.

In addition, Prior to each treatment, Solius software will prompt the user with the following questions to assess erythema:

- 1. Did you observe any pinkness (similar to sunburn) after your last treatment? (yes / no)
- 2. Did the pinkness last for more than 3 days? (yes / no)

3. Did you experience any pain or discomfort (excluding itch) with the pinkness? (none / mild / moderate/ severe)

Based on the user's response, the software could maintain current dose, reduce dose, or block account for further investigation. The PI or [name] or [name] will be notified to perform further assessment if an account was blocked by the software.

Side effect	Signs/symptoms	Instruction for subjects on
		monitoring
Sunburn	Pain, tenderness of the	Check for pain and redness 4-6
	skin, redness, tightness,	hours after treatment. If there
	itching, and rarely	is severe pain, should seek
	blistering	medical attention.
		If there are blisters, should seek
		medical attention
Photoaging	Atrophic skin, coarseness,	If there is increased fragility (i.e.
	fibrotic areas, increased	easy bruising or tearing of skin),
	fragility, laxity, mottled	then should seek medical
	pigmentation,	attention. The other
	telangiectasias, wrinkling	photoaging side effects are
		benign and more of a cosmetic
		nature.
Tanning	Skin darkening	As a benign side effect, no
		subject monitoring is needed

The following known side effects of UVB will be monitored:

# 10.3 Reporting Plans

[name] will serve as an Independent Scientific Reviewer (ISR). He will provide an assurance that the findings and conclusions reached are supported by the data presented, and also, to assure that the content is consistent with applicable scientific standards and will be responsible for a review of the data analysis, data interpretation and/or presentations and manuscripts.

The Principal Investigator at BMC/BU Medical Campus will report Unanticipated Problems, safety monitors' reports, and Adverse Events to the BMC/BU Medical Center IRB in accordance with IRB policies:

- Unanticipated Problems occurring at BMC/BU Medical Campus involving a fatal or life-threatening event will be reported to the IRB within 2 days of the investigator learning of the event.
- Unanticipated Problems occurring at BMC/BU Medical Campus not involving a fatal or lifethreatening event will be reported to the IRB within 7 days of the investigator learning of the event.
- Reports from safety monitors with recommended changes will be reported to the IRB within 7 days of the investigator receiving the report.
- Adverse Events (including Serious Adverse Events) will be reported in summary at the time of continuing review, along with a statement that the pattern of adverse events, in total, does not suggest that the research places subjects or others at a greater risk of harm than was previously known.
- Reports from safety monitors with no recommended changes will be reported to the IRB at the time of continuing review.

# 10.4 Stopping Rules

A subject will be withdrawn from the study if refuse to participate, or if the subject undergoes an adverse reaction to the light source e.g. skin erythema or pruritus.

# 11 Data Handling and Record Keeping

## 11.1 Confidentiality

Subjects are assigned a code after consent and enrolled in the study. All coded records containing subject information will be stored in [name] offices under lock and key. The blood samples will be kept in the [name] lab (M-1011). The door to the Vitamin D lab is accessed by those who have ID access to the lab. The data will be coded and after 7 years will be deidentified and kept indefinitely. Electronic information will be stored on a departmental server ("Y"drive) and "C" drive of study coordinator's computer both of which are password protected. Paper records will be stored in a locked room for which only study staff will have access to. Master list will be stored on the study coordinator's PC and will not be stored with study data. All other electronic data will be on the PC of the study coordinator, which is password protected. Paper master list will be stored and locked in M1013; only study staff and study coordinator have access to this room. All locations where data will be kept are inaccessible to the public. Data will be available only to study personnel. Data will be kept in a locked room. Study code will be used for all study data that is collected. The study coordinator and study staff will keep the subject list on their computer, which is password accessible only.

The study monitor or other authorized representatives of the sponsor may inspect all documents and records required to be maintained by the investigator, including but not limited to, medical records (office, clinic, or hospital) and pharmacy records for the subjects in this study. The clinical study site will permit access to such records.

## 11.2 Source Documents

Data generated by the methods described in the protocol will be recorded in the subjects' medical records and/or study progress notes. Data may be transcribed legibly on CRFs supplied for each subject or directly inputted into an electronic system or any combination thereof.

## 11.3 Case Report Forms

The study case report form (CRF) will be the primary data collection instrument for the study. All data requested on the CRF will be recorded. All missing data will be explained. If a space on the CRF is left blank because the procedure was not done or the question was not asked, "N/D" will be written. If the item is not applicable to the individual case, "N/A" will be written. All entries will be printed legibly in black ink. If any entry error has been made, to correct such an error, a single straight line will be drawn through the incorrect entry and the correct data will be entered above it. All such changes will be initialed and dated. There will be no erasures or white-out on CRFs. For clarification of illegible or uncertain entries, the clarification will be printed above the item, then initialed and dated.

See the Appendix for the following CRFs: Study Visit Report Form

# 11.4 Study Records Retention

All coded records containing subject information will be stored in [name] offices under lock and key. The blood will be kept in the [name] lab (M-1021A). The door to the Vitamin D lab is accessed by those who have ID access to the lab. The blood samples and data will be de-identified and kept indefinitely. They may be used for possible additional research in the future. Electronic information will be stored on a departmental server ("Y"drive) and "C" drive of study coordinator's computer both of which are password protected. Paper records will be stored in a locked room for which only study staff will have access to. Master list will be stored on the study coordinator's PC and will not be stored with study data. All other electronic data will be on the PC of the study coordinator, which is password protected. Paper master list will be stored and locked in M1013; only study staff and study coordinator have access to this room. All locations where data will be kept are inaccessible to the public. Data will be available only to study personnel. Data will be kept in a locked room. Study code will be used for all study data that is collected. The study coordinator and study staff will keep the subject list on their computer, which is password accessible only. Study records will be retained for at least seven years after completion of the study. Documentation of informed consent of subjects will be retained for at least seven years after the study is closed, unless the IRB waived the requirement for informed consent or documentation of informed consent. Such records may be preserved in hardcopy, electronic or other media forms and must be accessible for inspection and copying by authorized individuals.

# 12 Statistical Plan

The endpoint is the difference in vitamin D insufficiency/sufficiency prevalence between the treatment and the control group use at 16 weeks of follow-up. The subject will have at least one serum 25(OH)D

evaluation within 16 weeks, and at least one phototherapy session in the 16 weeks follow up. The protocol includes a sample size calculation, which allowed for a loss to follow-up of 15%.

Statistical analysis will be performed using SPSS Statistics, version 25 (IBM Corporation). Age, sex, BMI, and Fitzpatrick skin type will be matched in two study groups. Two-sided P < .05 will be considered significant. All models will be developed according to the intention-to-treat principle. A supportive analysis will also be conducted on the per-protocol (PP) population.

The biological and clinical characteristics at enrolment will be presented, and all variables for the participants in the treatment and control groups will be compared at each follow-up using Fisher's exact test for categorical variables and a Mann–Whitney *U* test for continuous variables. For intergroup differences, 95% CIs will be also calculated. The endpoint, the proportion of subjects converting from vitamin D deficiency/insufficiency to vitamin D insufficiency/sufficiency at 16 weeks will be compared between groups using Fisher's exact test and logistic regression adjusting for skin types. Secondary analysis will be involved a comparison of changing in serum levels of 25(OH)D between groups using a Mann–Whitney *U* test and linear regression adjusting for skin types. A linear mixed model will be used to examine the relationship between phototherapy and serum 25(OH)D3 at different time points, adjusting for the baseline values and correlation of outcomes within individuals and season.

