When ultraviolet B (UVB) radiation (wavelength of 290-320 nm) from the sun is absorbed into the skin, it converts 7-DHC, which is predominantly located in the stratum spinosum and stratum basale, to previtamin  $D_3$  which is thermodynamically unstable. Over several hours it isomerizes into vitamin  $D_3$ . The vitamin  $D_3$  from the skin and the vitamin  $D_2$  from food and supplements enters the circulation and are hydroxylated in the liver by a 25-hydroxylase to become 25-hydroxyvitaminD (25(OH)D), which is the major circulating form of vitamin D. 25(OH)D is hydroxylated again in the kidneys by 1alphahydroxylase to become 1,25-dihydroxyvitamin D (1,25(OH)2D), which is the active form of vitamin D. When calcium levels are too high, 24-hydroxylase activity increases, hydroxylating C24 and making, 24,25-Dihydroxyvitamin D (24,25(OH)2D) and 1,24,25-trihydroxyvitamin D (1,24,25-(OH)3D). This step begins the process of the degradation of both metabolites into inactive water-soluble metabolites that can be excreted in the bile. The ability to maintain 25(OH)D levels via sun exposure is influenced by the zenith angle of the sun. The zenith angle is defined as the oblique angle between the sun's rays and the earth's surface. The time of day, season, and latitude on the earth's surface all affect the zenith angle. Above 37° latitude during the months of November through February, there is a significant decrease in the amount of UVB photons hitting the earth's surface, as much as 80%-100% depending on latitude . Thus, for those living in areas at a zenith angle incompatible for producing vitamin D in the winter, they need to obtain their vitamin D via supplements and/or food containing or fortified with vitamin D.

Those living above 37° latitude during the months of November through February could also rely on artificial UVB light sources such as the Sperti lamp or UVB emitting LEDs. These lights permit the skin to convert 7-dehydrocholesterol into vitamin D allowing the body to maintain adequate vitamin D levels while avoiding exposure to the sun. In particular, these lights are resourceful to those having fat

malabsorption disorders such as Crohn's disease, cystic fibrosis, and/or gastric bypass. For these individuals who are unable to absorb vitamin D from the diet, exposure to UVB is the primary way of maintaining an adequate vitamin D status.

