Blood samples will be obtained from all subjects (cases and controls) at the screening visit and monthly throughout the 16 weeks of the study duration (weeks 1, 5, 9, 13, 17, 21), and weekly after the 16-week intervention for 4 weeks (week 22 - 25). Blood samples will be sent to Quest Diagnostics for determining the serum 25(OH)D levels. The study design summarized in Figure 1 and Table 2

If a subject needs to end his/her regiment early they will be able to do so, with no change to the study procedure. We will require a final blood sample collection from the study subject prior to his/her removal.

We anticipate the entire study will take 12 months to complete 16-week treatment for case group. As discussed earlier the study subject's involvement will last 26 weeks from screening to completion include one week for screening, 5 weeks for titration, 16 weeks for treatment and 4 weeks of post-treatment serum 25(OH)D monitoring.

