## 12.2 Sample Size Determination

The endpoint of this study is to compare the improvement of vitamin D status between treatment group and the controls. A previous study by Chandra et al. demonstrated the increase in the mean serum 25(OH)D in subjects with malabsorption syndrome receiving UV therapy from 21± 3 ng/mL to 27±4 ng/mL after 8 weeks (13). We would expect that to increase the serum 25(OH)D level by 10 ng/mL (SD=5ng/ml), after 16 weeks based on a previous study (13) as well as an earlier pilot study that was completed by Solius.

The endpoint is to improve vitamin D status in the treatment group compared to sham controls. We expect that the serum levels of 25(OH)D will increase more than 10 ng/ml (SD=5ng/ml) after 16 weeks of intervention in the treatment group compared to controls. Subjects converted from vitamin D deficient/insufficient to insufficient/sufficient is considered a minimum clinical important difference (MCID). We expect at least 70% of vitamin D deficient/insufficient subjects in the treatment group to convert to insufficient/ sufficient. Also, because of seasonal variations and other confounders, we expect maximum 30% of subject convert to insufficient/sufficient in sham control. With the desired power of 80% and significance level ( $\alpha$ ) of 0.01, the sample size in each group is 35.

Approximately 100 adult subjects with 5 skin types group (I, II, III, IV and V/VI) will be enrolled for vitamin D deficiency/ insufficiency screening. We expect that at least 80% of the population in the

Boston area has a level of 25(OH)D below 30 ng/ml. Thus, we will enroll 100 subjects with different skin types to enroll 80 vitamin D deficient or insufficient subjects in this study. We plan to match treatment and control group for age, sex, BMI and skin type by stratified random sampling (40 subjects in each group). In our experience, the rate of screen failure and subject dropout is 10-15%. Then, we expect to have at least 35 subjects per each group.

Parameters	Value
Conversion of the subjects from vitamin D deficient to vitamin D	70%
insufficient/sufficient or vitamin D insufficient to vitamin D sufficient in the	
treatment group after 16 weeks (P1)	
Conversion of the subjects from vitamin D deficient to vitamin D	30%
insufficient/sufficient or vitamin D insufficient to vitamin D sufficient in the control	
group after 16 weeks (P2)	
Significant level	0.01
Power	80%

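### Season is named as a cause of sham conversion but is left out of the conversion and 25(OH)D-change regressions, which forgoes precision and leaves chance season imbalance in the estimate

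*Combined protocol and SAP*

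**What the plan says.** - **Season as a cause.** Sections 4.1, 12.1 and 12.2 all give season as a reason for conversion without UVB treatment. In Section 12.2: "because of seasonal variations and other confounders, we expect maximum 30% of subject convert to insufficient/sufficient in sham control". That 30% is the control rate in the sample size formula.
- **Why season matters.** Section 3.1: "Above 37° latitude during the months of November through February, there is a significant decrease in the amount of UVB photons", with a loss put as high as 80–100% depending on latitude. Section 5 places the study in Boston, which I take to lie above 37°.
- **Conversion endpoint.** Section 12: it "will be compared between groups using Fisher's exact test and logistic regression adjusting for skin types".
- **25(OH)D change.** Section 12: a Mann–Whitney test and "linear regression adjusting for skin types".
- **Repeated 25(OH)D.** Section 12: a linear mixed model "adjusting for the baseline values and correlation of outcomes within individuals and season". This is the only analysis that includes season, and no coding of season is given.
- **Randomisation.** Sections 5 and 12.2 stratify by age, sex, BMI and skin type. Entry date is not a factor.
- **Calendar.** Section 9: "We anticipate the entire study will take 12 months to complete 16-week treatment for case group". The same section gives each subject 26 weeks of participation.

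**The concern.** The plan treats season as strong enough to help explain a 30% sham conversion rate and to need adjustment in the mixed model. It then leaves season out of the analysis of the endpoint on which the trial is sized. The mixed model cannot make up for this, because it analyses concentration over time and not conversion.

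Entry dates will differ. Twelve months less 26 weeks per subject leaves an entry window of up to about 26 weeks. Week 1 to Week 21 spans 20 weeks, longer than the roughly 17 weeks from November to February, so how much natural UVB falls within a subject's follow-up depends on when that subject starts. If one arm happens to start more often at a favourable time, the observed conversion difference moves with it, and neither the design nor the endpoint model takes that out.

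**Working it through.** **1. The plan's own figure.** Section 12.2 uses 70% v 30%, 80% power and alpha 0.01 two-sided:

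N = (2.58 × √0.5 + 0.84 × √0.42)² / 0.4² = (1.824 + 0.544)² / 0.16 = 35.07.

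The stated 35 per group is reproduced (36 if rounded up). Section 12 sets the analysis alpha at 0.05, so both levels are shown below.

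**2. Assumptions.** The documents give no season-specific conversion rates and no recruitment start date. I assume half the subjects in each of two seasons, with overall rates kept at 30% and 70%:

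- 20-point gap: sham 20%/40%, UVB 60%/80%.
- 40-point gap: sham 10%/50%, UVB 50%/90%.

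**3. Chance imbalance.** The SD of the between-arm difference in season share is √(0.25 × 2/35) = 0.12.

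- 20-point gap: 1-SD shift in the conversion difference 0.20 × 0.12 = 2.4 points; 95% range ±4.7.
- 40-point gap: 0.40 × 0.12 = 4.8 points; 95% range ±9.4.
- With an 80/20 season split the imbalance SD falls to √(0.16 × 2/35) = 0.096.

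**4. Share of the sampling error.** The unadjusted standard error is √(2 × 0.21/35) = 11.0 points, and it already contains the season component. Within season the average binomial variance is 0.20 (20-point gap) or 0.17 (40-point gap), giving √(2 × 0.20/35) = 10.7 and √(2 × 0.17/35) = 9.9 points. That reduction is the precision forgone.

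**5. Power of the logistic likelihood-ratio test.** 35 per arm, about 4,000 simulated trials per scenario, skin type left out of both models:

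| Season gap | alpha 0.01, without → with season | alpha 0.05, without → with season |
|---|---|---|
| none | 0.82 → 0.82 | 0.93 → 0.93 |
| 20 points | 0.82 → 0.84 | 0.92 → 0.94 |
| 40 points | 0.81 → 0.90 | 0.92 → 0.97 |

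With skin type in both models, power at alpha 0.01 goes from about 0.80 to 0.83, 0.86 and 0.90 for gaps of 20, 30 and 40 points. At 0.05 it goes from about 0.92 to 0.94–0.98. If the true effect is only 50% v 30% with a 40-point gap, power at 0.05 is 0.40 without season and 0.47 with it.

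**6. One unlucky allocation.** Take a 40-point gap, with 14/35 UVB and 21/35 sham subjects in the favourable season.

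- UVB: (14 × 0.9 + 21 × 0.5)/35 = 66%.
- Sham: (21 × 0.5 + 14 × 0.1)/35 = 34%.
- Unadjusted difference 32 points; season-adjusted 40 points.
- Power at 0.01 is 0.58 without season and 0.90 with it.

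An imbalance at least this large against the device has roughly a 6% chance.

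**7. Type I error.** Under the null with a 40-point gap, the logistic test without season rejects 0.056 of the time at 0.05, and with season 0.052. Fisher's test rejects 0.028.

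**8. 25(OH)D change.** Section 12.2 plans 10 ng/mL with SD 5. A 5 ng/mL season gap (±2.5, assumed) would cut the residual SD to √(25 − 6.25) = 4.3, and chance imbalance could shift the difference by 1.96 × 0.12 × 5, about 1.2 ng/mL. Power at the planned effect exceeds 0.999 at alpha 0.01 either way.

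**The case against.** Three stronger readings are tempting, and the documents support none of them.

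- **Season biases the comparison.** Allocation is randomised, so any imbalance is chance error. Type I error averaged over randomisations stays close to nominal (step 7), and the planned 95% confidence intervals already cover this variation.
- **The trial is underpowered because season is ignored.** The 70% and 30% are overall rates that already include season, so the skin-type-only model delivers about the planned 80% at alpha 0.01. What is lost is a possible gain.
- **The plan ignores season.** It does not: the mixed model adjusts for it. For 25(OH)D as a continuous outcome that covers much of the ground, and power there is not in question.

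The size of the gain is also open to challenge. If SD 5 ng/mL is the whole spread of change, a ±2.5 drift leaves a residual SD of 4.33. With baselines spread evenly over 10–30 ng/mL and cut-offs at 20 and 30 (both assumed), sham conversion is then 8% v 32%, a 24-point gap. A ±5 drift has variance 25 and would use up the entire SD, so gaps near 50 points are hard to reconcile with the plan, and 40 points is towards the upper end. An uneven season split reduces the gain further.

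Finally, Fisher's exact test is listed for the same endpoint and cannot take a covariate. If it decides the trial, adding season to the logistic model leaves the main answer unchanged. All of this stands. It limits the size of the point and shapes the fix, but it does not explain why a factor adjusted for in the mixed model is absent from the endpoint model.

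**Conclusion.** The point holds as a worthwhile, low-cost improvement in precision, and the change should be made before unblinding. Neither stratification nor the endpoint model controls a factor that the protocol itself says drives sham conversion. At the planned effect the power gain is about 2 to 10 points at alpha 0.01 and about 1 to 6 points at 0.05. The protection matters most when the allocation happens to be unbalanced by season. For 25(OH)D change the benefit is precision and consistency with the mixed model. These sizes rest on assumed season gaps of 20–40 points and an even season split, since the documents give neither.

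**What to change.** In Section 12:

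1. Add season, derived from the Week 1 date, as a prespecified covariate in the logistic regression for conversion and in the linear regression for change. Use the same coding in the mixed model.
2. Fix one coding that varies over the actual entry window: a sine/cosine pair of the Week 1 date (two degrees of freedom), or a split chosen from the recruitment calendar before unblinding. A fixed November–April v May–October split could be nearly constant over a window of about 26 weeks.
3. Name the logistic model adjusted for season and skin type as the primary test of conversion. Report a standardised risk difference with 95% CI, and keep Fisher's exact test as supportive.

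**Cost.** A few lines of SAP text and a visit date the trial holds anyway. One or two degrees of freedom are spent, with almost no power loss if season has no effect. The odds ratio becomes conditional on season: in the 40-point scenario it is (0.7/0.3)/(0.3/0.7) = 5.4 overall and (0.5/0.5)/(0.1/0.9) = 9 within season, which is why the standardised risk difference should be reported. Stratifying by entry period is an alternative, but four factors are already planned for 80 subjects.

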# 3 Background/Rationale & Purpose

# 3.1 Background Information

Vitamin D deficiency has been a worldwide health problem for over a century, now affecting over 1 billion people on this planet. Although technology is drastically advancing, we still are unable to put an end to this health emergency.

Vitamin D can be introduced in the body in two ways, 1) via diet and 2) through the sun. Few foods naturally contain vitamin D (either  $D_2$  or  $D_3$ ) such as oily fish. For instance fresh wild salmon (3.5oz or

100g) has between 600-1000 IU of vitamin D3. Canned tuna (3.6oz or 102 g) has about 230 IU of vitamin D3. Sun-dried mushrooms and egg yolks are also viable sources of vitamin D. Sun-dried shiitake mushrooms have about 1600 IU of vitamin D2 whereas egg yolks have about 20 IU of vitamin D2 or vitamin D3. There are some fortified foods that also contain vitamin D; fortified milk and fortified orange juice each has about 100 IU/8 oz of vitamin D3. Some cereals, such as Quaker Oatmeal has as much as 40 IU vitamin D/cup. Margarine has about 60 IU of vitamin D/tablespoon. In a study that looked at the plasma levels of 25(OH)D3 amongst fish eaters and non-fish eaters (vegans and vegetarians), those who did not consume fish had lower levels of 25(OH)D3 in both the summer months (20%) and winter months (38%). Thus the consumption of fish in the diet is critical in maintaining vitamin D status throughout the year, especially during the winter months.

When assessing the optimal dietary intake of vitamin D, there might be some controversy as to which guideline to follow. The Institute of Medicine (IOM) issued guidelines to maintain adequate serum 25(OH)D levels above 20 ng/mL. The Endocrine Society's guidelines reflect the needs to treat and prevent vitamin D deficiency and maintain a 25(OH)D status above 30 ng/mL. One would have to consume a significant amount of fish and fortified food products to meet the above recommendations. Thus, it is critical that we incorporate sun exposure into our everyday lives, and/or take vitamin D supplements.

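### Name one deciding test for the conversion endpoint: Section 12 lists Fisher's exact test and a skin-adjusted logistic model, which differ in level and power, and ranks neither

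*Combined protocol and SAP*

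**What the plan says.** Section 12 (Statistical Plan) states the endpoint as a difference in proportions: "The endpoint is the difference in vitamin D insufficiency/sufficiency prevalence between the treatment and the control group" at 16 weeks. Conversion is to be compared by Fisher's "exact test and logistic regression adjusting for skin types". The significance rule is "Two-sided P < .05 will be considered significant". Section 12 does rank other analyses: per-protocol is supportive and change in 25(OH)D is secondary. Nowhere in the document are the two conversion tests ranked, and there is no rule for when they disagree.

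Change in 25(OH)D is compared by a Mann-Whitney "test and linear regression adjusting for skin types". Baseline appears as a covariate only in the linear mixed model, "adjusting for the baseline values and correlation of outcomes within individuals and season".

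The parameter table in Section 12.2 counts conversion from each subject's own starting category: from deficient to "insufficient/sufficient or vitamin D insufficient to vitamin D sufficient in the" group concerned. The same section assumes 70% v 30% conversion and 35 evaluable of 40 randomised per arm. It also says "We expect that the serum levels of 25(OH)D will increase more than 10 ng/ml (SD=5ng/ml) after 16 weeks".

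**The concern.** Section 3.2 says the FDA requires a study with statistical significance, so which P value counts is the result of the trial. The two tests answer nearly the same question, but not with the same level or power. If either may be quoted, the logistic test in effect governs. If both must be significant, Fisher's test in effect governs. The plan allows both readings, and a choice made after unblinding would not be credible.

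A second, lesser matter is that a subject's starting 25(OH)D largely determines how far the level must rise to convert. If the cut-offs are 20 and 30 ng/mL, a rise of 1 is enough from 29 but 9 is needed from 21. The plan collects this value and uses it in the mixed model, but not as a covariate in either conversion test or in the change regression.

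**Working it through.** **Inputs.** From Sections 12 and 12.2: 70% v 30% conversion, two-sided P < .05 for analysis, 0.01 for sample size, 80% power, 40 randomised and 35 evaluable per arm, five skin groups. Section 5 gives stratified randomisation, which supports roughly balanced skin groups. The size of any skin-type effect on conversion is not given. It was assumed to run from none to a log-odds spread of -1.5 to +1.5 over five equal groups.

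**The plan's own figure.** With the Section 12.2 formula and its rounded z values:

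N = {2.58 × √(0.5 × 0.5 × 2) + 0.84 × √(0.21 + 0.21)}² / 0.4² = (1.824 + 0.544)² / 0.16 = 35.07.

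The stated 35 is reproduced (36 with unrounded z). The formula is for an unadjusted comparison of two proportions.

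**Exact enumeration, no skin adjustment, P < .05.** Each pair of converter counts is weighted by its binomial probability. Both tests are applied, and the probability that only the likelihood-ratio (LR) test is significant is summed.

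| True rates | Per arm | Fisher rejects | LR rejects | LR only |
|---|---|---|---|---|
| 70% v 30% | 35 | 88.2% | 92.6% | 4.4% |
| 70% v 30% | 40 | 94.1% | 96.4% | 2.3% |
| 60% v 30% | 35 | 62.3% | 72.0% | 9.7% |
| 60% v 30% | 40 | 72.5% | 79.7% | 7.2% |
| 50% v 30% | 35 | 31.2% | 41.6% | 10.4% |
| 50% v 30% | 40 | 36.8% | 46.1% | 9.3% |
| 30% v 30% | 35 | 2.8% | 5.6% | 2.8% |
| 30% v 30% | 40 | 2.8% | 5.4% | 2.6% |

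Fisher's test was never significant alone. One example at 35 per arm: 20 v 11 converters (57.1% v 31.4%) gives Fisher P = 0.053 and LR P = 0.029.

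**Simulation with the skin-adjusted model, P < .05, 5,000-8,000 trials per setting.**

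- 70% v 30%, balanced skin groups: logistic significant and Fisher not in 5.2-6.9% of trials at 35 per arm and 2.0-3.3% at 40. With 40 randomised and 5 lost at random per arm: 5.3-6.5%.
- 50% v 30%: about 13-17%.
- Reverse disagreement: with balanced groups, only in trials where separation breaks the Wald test (about 0.1%, up to 0.3% with a strong skin effect). With unbalanced groups, about 0.2-0.9% at 35 per arm and 0.3-0.4% at 40.
- No effect: Fisher rejects in about 2-3%, the ordinary LR logistic test in 5.4-6.8%.

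**Gain from baseline.** These figures compare a Firth logistic model with skin type only against one that adds starting category and baseline value, at 0.05. They assume cut-offs of 20 and 30, baseline uniform over 10-30 or 15-30 ng/mL, and change independent of baseline.

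| Scenario | Gain in power |
|---|---|
| 70/30 with SD 5 (implies a difference of only 6.0-6.1 ng/mL) | +1.2 to +3.3 points |
| 70/30 with SD 7 (difference 7.9-8.0) | +0.4 to +1.9 |
| 70/30 and 10 ng/mL both kept (SD about 9.1) | -0.2 to +1.6 |
| 10 ng/mL and SD 5 kept, sham 30% (treated 88-89%) | 0 to +0.2 |

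Under the null, the Firth test with baseline rejected in 4.4-5.3%. The ordinary LR test of the same model rejected in 6.2-7.3%.

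**The case against.** The strongest reply is that the tests agree in well over 90% of trials if the planned effect is real, that Fisher's test matches the unadjusted comparison used to size the trial, and that one sentence settles the matter. All of that stands. It supports a short fix, not silence.

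It can also be said that baseline adjustment is a preference. This largely stands. Under the plan's own 10 ng/mL and SD 5 the gain is close to nil, and the cut-offs and baseline range behind every gain figure are assumed. Section 12 already promises 95% CIs for differences between groups, so interval reporting is not absent.

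A reader might infer several stronger points that the documents do not support:

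- That leaving out baseline biases the comparison. It does not; allocation is randomised and only precision is lost.
- That baseline is ignored. It enters the definition of conversion and of change; only the covariate is missing.
- That the logistic test is always the more favourable one. That holds for the LR form with balanced strata. Section 12 does not name a form, and rare reversals occur with Wald tests or unbalanced groups.
- That the sponsor means to quote the better P value. Nothing in the plan says so; it is simply silent.

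**Conclusion.** The concern holds in limited form. Two tests with different levels stand as the verdict on the only named endpoint, and neither is made deciding. At 70% v 30% they split in about 5-7% of trials at 35 per arm and 2-3% at 40, nearly always with the logistic test significant and Fisher's not. The split grows if the true effect is smaller. These figures rest on P < .05, five roughly balanced skin groups and an assumed skin effect, and they are not general rates. Null rejection of about 2-3% v 5-7% shows that the missing rule also fixes the type I error rate. The lack of a baseline covariate costs nil to about 3 points of power at 0.05, depending on the SD of change. This should be fixed before unblinding, but it does not undermine the design.

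**What to change.** Before unblinding, name one deciding primary analysis for conversion and its test form, and label the other supportive.

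Preferred: a logistic model with treatment, skin type and baseline 25(OH)D, tested by Firth penalised likelihood or by permutation within skin-type strata. Report an adjusted risk difference with 95% CI, which is the scale on which Section 12 states the endpoint. Fisher's test then becomes supportive. Add baseline 25(OH)D to the change regression as well. If the team wants no baseline terms in the primary test, it should still name one deciding test.

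Cost: a few lines of text and no new data. The larger model, with starting category as well as value, has seven terms plus an intercept (1 treatment, 4 skin, 2 baseline) on about 35-40 converters in the whole trial (0.7 × 35 + 0.3 × 35 = 35; 40 with 40 per arm). That is why Firth or permutation is advised over the ordinary test. Check that the software named in Section 12 can run it, or name other software.

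Three separate wording items:

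- State the deficient/insufficient cut-off for the endpoint. Section 3.1 mentions 20 ng/mL only as background ("issued guidelines to maintain adequate serum 25(OH)D levels above 20 ng/mL").
- Say which sample, screening or Week 1, sets the starting category, and what happens if the Week 1 value is 30 or more.
- Reconcile Section 4.1.1, which puts the baseline sample just before the first exposure, with the note under the compensation table in Section 6.2, which puts blood collection after each exposure.
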